4.8 Blinding/Unblinding

Not applicable.

4.9 Treatment Compliance

Treatment compliance will be monitored by drug accountability as well as the subject's medical record and eCRF.

4.10 Destruction or Return of Investigational Product

For this study, IP (those supplied by BMS, a vendor or sourced by the investigator) such as partially used study drug containers, vials and syringes may be destroyed on site.

If	Then
IP supplied by BMS (including its vendors)	Any unused IP supplied by BMS can only be destroyed after being inspected and reconciled by the responsible Study Monitor unless IP containers must be immediately destroyed as required for safety, or to meet local regulations (e.g., cytotoxics or biologics). If IP will be returned, the return will be arranged by the responsible Study Monitor.
IP sourced by site, not supplied by BMS (or its vendors) (examples include IP sourced from the sites stock or commercial supply, or a specialty pharmacy)	It is the investigator's or designee's responsibility to dispose of all containers according to the institutional guidelines and procedures.

It is the investigator's or designee's responsibility to arrange for disposal, provided that procedures for proper disposal have been established according to applicable federal, state, local, and institutional guidelines and procedures, and provided that appropriate records of disposal are kept. The following minimal standards must be met:

- On-site disposal practices must not expose humans to risks from the drug.
- On-site disposal practices and procedures are in agreement with applicable laws and regulations, including any special requirements for controlled or hazardous substances.
- Written procedures for on-site disposal are available and followed. The procedures must be filed with the site's SOPs and a copy provided to BMS upon request.
- Records are maintained that allow for traceability of each container, including the date disposed of, quantity disposed, and identification of the person disposing the containers. The method of disposal, i.e., incinerator, licensed sanitary landfill, or licensed waste disposal vendor must be documented.
- Accountability and disposal records are complete, up-to-date, and available for the Monitor to review throughout the clinical trial period.

It is the investigator's or designee's responsibility to arrange for disposal of all empty containers.

If conditions for destruction cannot be met, the responsible Study Monitor will make arrangements for return of IP provided by BMS (or its vendors). Destruction of non-IP sourced by the site, not supplied by BMS, is solely the responsibility of the investigator or designee.

Please refer to Section 9.2.2 for additional guidance on IP records and documentation.

4.11 Retained Samples for Bioavailability/Bioequivalence/Biocomparability Not applicable.

5 STUDY ASSESSMENTS AND PROCEDURES

5.1 Flow Chart/Time and Events Schedule

Table 5.1-1: Screening Procedural Outline - All Subjects (CA209649)				
Procedure	Screening Visit	Notes		
Eligibility Assessments				
Informed Consent	X	Contact IRT to obtain study subject number. Study allows for re-enrollment of a subject that has discontinued the study as a pre-treatment failure. If re-enrolled, the subject must be re-consented and assigned a new subject number from IRT.		
Inclusion/Exclusion Criteria	X	All inclusion/exclusion criteria should be assessed during screening and confirmed prior to randomization.		
Disease Status	·	·		
Medical History	X	-		
Tumor Tissue Samples	X	Recent sample or archival. Sufficient tumor tissue (either a formalin-fixed, paraffin-embedded [FFPE] tissue block or minimum 20 positively charged slides*) must be available within 6 months prior to randomization and sent to a central laboratory for biomarker analysis. PDL1 status must be assessed prior to randomization.		
		Tissue must be a core needle biopsy, excisional biopsy, or incisional biopsy. Fine needle biopsies are not considered adequate for biomarker review and randomization. Biopsies of bone lesions that do not have a soft tissue component or decalcified bone tumor samples are also not acceptable.		
		* If, despite best efforts, a minimum 20 slides are not obtainable, discuss with Sponsor.		
Safety Assessments				
Physical Examination	X	Within 14 days prior to randomization.		
Physical Measurements	X	Include Height, Weight and BSA. Within 14 days prior to randomization.		
Vital Signs	X	Obtain vital signs at the screening visit and within 72 hours prior to first dose. Including BP, heart rate, and temperature.		

Revised Protocol No.: 09

Date: 16-Sep-2019

Table 5.1-1: Screening Procedural Outline - All Subjects (CA209649)					
Procedure	Screening Visit	Notes			
Performance Status (ECOG)	X	Within 14 days prior to randomization. See protocol Appendix 3.			
Assessment of Signs and Symptoms	X	Within 14 days prior to randomization.			
Serious Adverse Event (SAE) Assessment	X	After informed consent is signed.			
Review of concomitant medications	X	Within 28 days prior to randomization.			
Electrocardiogram (ECG)	X	Within 14 days prior to randomization.			
Laboratory Tests	X	On site/local complete blood count (CBC) w/differential, chemistry panel including: LDH, AST, ALT, ALP, total bilirubin, blood urea nitrogen (BUN) or serum urea level, creatinine, Ca, Na, K, Cl, fasting glucose and albumin within 14 days prior to randomization. Endocrine panel (TSH, Free T4, Free T3; Total T3/T4 are acceptable if Free T3/T4 are not available), Hep B/C (HBV HBsAG, HCV antibody or HCV RNA), within 28 days prior to randomization.			
Pregnancy Test (WOCBP only)	X	Serum or urine to be done at screening visit and repeated within 24 hours prior to first dose of study drug.			
Efficacy Assessment		·			
Baseline Tumor Imaging Assessment	X	CT/MRI scan of chest, abdomen, pelvis and any clinically indicated sites within 28 days prior to randomization. CT/MRI scan prior to ICF signature might be acceptable if performed within 28 days prior to randomization.			
IRT					
IRT contact	X	The IRT must be contacted for subject number assignment at the time informed consent is obtained.			

Table 5.1-2: On	Table 5.1-2: On-Treatment Assessments - Subjects in Nivolumab-plus-Ipilimumab Arm (CA209649)				
Procedure	Cycle 1 Day 1 (3-week cycle) C1D1	Cycles 2 - 4 (Every 3 weeks) on Day 1	Cycle 5 and beyond (Every 2 weeks) on Day 1 ^a	Note *Treatment till PD, unacceptable toxicity, withdraw from IC	
Safety Assessments					
Physical Examination	X	X	X	To be performed within 72 hours of dosing.	
Vital Signs	X	X	X	Obtain vital signs within 72 hours prior to dose. Including BP, heart rate, and temperature.	
Weight and ECOG Performance Status	X	X	X	Within 72 hours of dosing. See protocol Appendix 3 for ECOG Performance Status scale.	
Adverse Events Assessment		Continuously		Assessed using NCI CTCAE v.4	
Serious Adverse Event (SAE)		Continuously		Assessed using NCI CTCAE v.4	
Review of concomitant medications	X	X	X	-	
Laboratory Tests	See Note	See Note	See Note	Within 72 hours prior to each dose through Week 23 visit and every alternate dose thereafter.	
				Include CBC w/differential, ALT, AST, total bilirubin, BUN or serum urea level, creatinine, Ca, Na, K, Cl, LDH and glucose.	
				TSH (with reflexive Free T4 and Free T3; Total T3/T4 are acceptable if Free T3/T4 are not available) every 6 weeks (± 7 days) starting at C1D1.	
				Note: Laboratory tests do not need to be repeated on C1D1 if performed within 14 days prior to first dose.	
Pregnancy Test (WOCBP only)	X	See Note	See Note	Serum or urine within 24 hours prior to the initial administration of study drug and then every 4 weeks (± 7 days) regardless of dose delays; if collected with a dosing visit, then obtain within 24 hours prior to administration of study drug: urine or serum.	

Table 5.1-2: On	-Treatment Asses	ssments - Subject	ts in Nivolumab-plu	us-Ipilimumab Arm (CA209649)
Procedure	Cycle 1 Day 1 (3-week cycle) C1D1	Cycles 2 - 4 (Every 3 weeks) on Day 1	Cycle 5 and beyond (Every 2 weeks) on Day 1 ^a	Note *Treatment till PD, unacceptable toxicity, withdraw from IC
PK and Immunogenicity Sam	ıpling			
PK samples		See Table	e 5.5-1 for details regard	ling specific sample timing.
Immunogenicity blood sample		See Table	e 5.5-1 for details regard	ling specific sample timing.
Efficacy Assessments				
Tumor Imaging Assessment		See Note	See Note	CT/MRI scan of chest, abdomen, pelvis, and any clinically indicated sites.
				Every 6 weeks (± 7 days) from first dose up to and including Week 48, then every 12 weeks (± 7 days) regardless of treatment schedule until disease progression (unless treatment beyond PD is permitted; see Section 4.5.1.6), or the subject withdraws consent, whichever comes first. Subjects who discontinue study treatment for reasons other than PD will continue to have tumor assessments until their disease progresses or they withdraw consent.
				Use same imaging method as was used at screening/baseline
Collection of biomarker sampling				
Outcomes Research Assessme	ents			
FACT-Ga	X			Assessed every 6 weeks (± 3 days) from C1D1, regardless
EQ-5D-3L	X	See Note	See Note	of treatment schedule; if administered on a dosing day, assessment should take place prior to any other study procedures.
Health Care Resource Utilization	X	X	X	

Procedure	Cycle 1 Day 1 (3-week cycle) C1D1	Cycles 2 - 4 (Every 3 weeks) on Day 1	Cycle 5 and beyond (Every 2 weeks) on Day 1 ^a	Note *Treatment till PD, unacceptable toxicity, withdraw from IC
Study Drug		•		
Randomization	X			Contact IRT for randomization Note: Randomization to the nivolumab plus ipilimumab arm was closed as of 05-June-2018
Dispense Study Treatment	X	X	X	First dose to be administered within 3 calendar days after randomization. See Table 4.5.1.1-1. Cycles 2 - 4: subsequent nivolumab and ipilimumab dose may be administered within 3 days before or after the scheduled date if necessary. Subjects may be dosed no less than 18 days between doses. Cycle 5 till EOT: nivolumab 240 mg may be administered up to 2 days before or 3 days after the scheduled date if necessary. Subjects may be dosed no less than 12 days between doses. Nivolumab 480 mg should be given 2 weeks following the last administration of nivolumab 240 mg. Nivolumab 480 mg may be administered up to 3 days before or 3 days after the scheduled date, if necessary. Subjects may be dosed no less than 25 days between doses. Vials may be assigned through IRT up to 3 calendar days prior to every dose date.

^a For subjects receiving nivolumab 480 mg Q4W alone, schedule of study procedures will be aligned with dosing visits (every 4 weeks on Day 1). Laboratory test should be done prior each dose. TSH (with reflexive Free T4 and Free T3; Total T3/T4 are acceptable if Free T3/T4 are not available) is acceptable to perform at alternative dose.

Table 5.1-3: On-Treatment Assessments - Subjects in Nivolumab-plus-Chemotherapy (XELOX or FOLFOX) Arm (CA209649)Nivolumab-Nivolumab-plusplus-XELOX Nivolumab-plus-**FOLFOX** and XELOX Note Cycle 2 and Nivolumab-Cycle 2 and **Procedure** *Treatment till PD, unacceptable toxicity, withdraw bevond beyond plusfrom IC (Every 2 weeks) **FOLFOX** (Every 3 weeks) on Day 1^a on Day 1 Cycle 1 Day 1 (C1D1)**Safety Assessments** X X X **Targeted Physical Examination** To be performed within 72 hours of dosing. X X Vital Signs X Obtain vital signs within 72 hours prior to dose. Including BP, heart rate and temperature. Weight, BSA and ECOG X X X Within 72 hours of dosing. See protocol Appendix 3 for Performance Status ECOG Performance Status scale Adverse Events Assessment Continuously Assessed using NCI CTCAE v.4 Assessed using NCI CTCAE v.4 Serious Adverse Event (SAE) Continuously Review of concomitant X X X medications Nivolumab + XELOX: Within 72 hours prior to each Laboratory Tests See Note See Note See Note dose. Nivolumab + FOLFOX: Within 72 hours prior to each dose through Week 23 and every alternate dose thereafter. Include CBC w/differential, ALT, AST, total bilirubin, BUN or serum urea level, creatinine, Ca, Na, K, Cl, LDH and glucose. TSH (with reflexive Free T4 and Free T3; Total T3/T4 are acceptable if Free T3/T4 are not available) every 6 weeks (\pm 7 days) starting at C1D1. Note: Laboratory tests do not need to be repeated on C1D1 if performed within 14 days prior to first dose.

Table 5.1-3: On-Treatment Assessments - Subjects in Nivolumab-plus-Chemotherapy (XELOX or FOLFOX) Arm (CA209649)					
Procedure	and XELOX FOL Cycle 2 and beyond beyond FOLFOX (Every 3 weeks)		Nivolumab-plus- FOLFOX Cycle 2 and beyond (Every 2 weeks) on Day 1 ^a	Note *Treatment till PD, unacceptable toxicity, withdraw from IC	
Pregnancy Test (WOCBP only)	X	See Note	See Note	Serum or urine within 24 hours prior to the initial administration of study drug and then every 4 weeks (± 7 days) regardless of dose delays; if collected with a dosing visit, then obtain within 24 hours prior to administration of study drug: urine or serum.	
PK and Immunogenicity Sampling					
PK samples	See Table 5.5-2 and Table 5.5-3 for details regarding specific sample timing.				
Immunogenicity blood sample		See Table 5.5-2 and Table 5.5-3 for details regarding specific sample timing.			

Table 5.1-3: On-Treatment Assessments - Subjects in Nivolumab-plus-Chemotherapy (XELOX or FOLFOX) Arm (CA209649)					
Procedure	Nivolumab- plus-XELOX and Nivolumab- plus- FOLFOX Cycle 1 Day 1 (C1D1)	Nivolumab-plus- XELOX Cycle 2 and beyond (Every 3 weeks) on Day 1	Nivolumab-plus- FOLFOX Cycle 2 and beyond (Every 2 weeks) on Day 1 ^a	Note *Treatment till PD, unacceptable toxicity, withdraw from IC	
Efficacy Assessments	1		1		
Tumor Imaging Assessment		See Note	See Note	CT/MRI scan of chest, abdomen, pelvis, and any clinically indicated sites. Every 6 weeks (± 7 days) from first dose up to and	
				including Week 48, then every 12 weeks (± 7 days) regardless of treatment schedule until disease progression (unless treatment beyond PD is permitted; see Section 4.5.1.6), or the subject withdraws consent, whichever comes first. Subjects who discontinue study treatment for reasons other than PD will continue to have tumor assessments until their disease progresses or they withdraw consent.	
				Use same imaging method as was used at screening/baseline	
Collection of biomarker sampling data					
Outcomes Research Assessments					
FACT-Ga	X			Assessed every 6 weeks (± 3 days) from C1D1, regardless	
EQ-5D-3L	X	See Note	See Note	of treatment schedule; if administered on a dosing day, assessment should take place prior to any other study procedures.	
Health Care Resource Utilization	X	X	X		

olumab- XELOX and	Nivolumab-plus-		
e 1 Day 1	XELOX Cycle 2 and beyond (Every 3 weeks) on Day 1	Nivolumab-plus- FOLFOX Cycle 2 and beyond (Every 2 weeks) on Day 1 ^a	Note *Treatment till PD, unacceptable toxicity, withdraw from IC
X			Contact IRT for randomization
X	X	X	First dose to be administered within 3 calendar days after randomization. Nivolumab and chemotherapy (XELOX or FOLFOX) should be administered on the same day. • Nivolumab dose schedule: in the nivolumab-plus-XELOX arm (every-3-week dosing), nivolumab may be administered within 3 days before or after the scheduled date if necessary, but subjects may be dosed no less than 18 days between doses; in the nivolumab-plus-FOLFOX arm (every-2-week dosing), nivolumab may be administered up to 2 days before or 3 days after the scheduled date if necessary, but subjects may be dosed no less than 12 days between doses. Nivolumab 480 mg should be given 2 weeks following the last administration of 240 mg, or 3 weeks following
	OLFOX le 1 Day 1 C1D1)	DLFOX (Every 3 weeks) on Day 1 C1D1) (Every 3 weeks) On Day 1	DLFOX (Every 3 weeks) (Every 2 weeks) on Day 1 on Day 1 X

Table 5.1-3: On-Treatment Assessments - Subjects in Nivolumab-plus-Chemotherapy (XELOX or FOLFOX) Arm (CA209649)Nivolumab-Nivolumab-plusplus-XELOX Nivolumab-plus-**FOLFOX** XELOX and Note Cycle 2 and Nivolumab-Cycle 2 and **Procedure** *Treatment till PD, unacceptable toxicity, withdraw bevond bevond plusfrom IC (Every 2 weeks) (Every 3 weeks) **FOLFOX** on Day 1 on Day 1a Cycle 1 Day 1 (C1D1)the scheduled date, if necessary. Subjects may be dosed no less than 25 days between doses. • XELOX dose schedule: see Table 4.6.1-1. Subsequent XELOX doses may be administered within dosing windows per package insert or local standard. • FOLFOX dose schedule: see Table 4.6.1-2. Subsequent FOLFOX doses may be administered within dosing windows per package insert or local standard. Vials may be assigned up to 3 calendar days prior to every dose date.

^a For subjects in nivo-plus-chemotherapy arm, a 480 mg Q4W nivolumab treatment regimen will be permitted when all chemotherapy is discontinued and nivolumab is continued alone, subjects in this arm must be in the study for a minimum of 6 months from Cycle 1, Day 1 before switching to 480 mg Q4W nivolumab. For subjects receiving nivolumab 480 mg Q4W alone, schedule of study procedures will be aligned with dosing visits (every 4 weeks on Day 1). Laboratory test should be done prior each dose. TSH (with reflexive Free T4 and Free T3; Total T3/T4 are acceptable if Free T3/T4 are not available) is acceptable to perform at alternative dose.

Table 5.1-4: On-Treatment Assessments - Subjects in Chemotherapy (XELOX or FOLFOX) Arm (CA209649)						
Procedure	dure XELOX and FOLFOX Cycle 1 Day 1 (C1D1) XELOX Cycle 2 and beyond (Every 3 weeks) on Day 1 FOLFOX Cycle 2 and beyond (Every 2 weeks) on Day 1		Note *Treatment till PD, unacceptable toxicity, withdraw from IC			
Safety Assessments						
Targeted Physical Examination	X	X	X	To be performed within 72 hours of dosing.		
Vital Signs	X	X	X	Obtain vital signs within 72 hours prior to dose. Including BP, heart rate and temperature.		
Weight, BSA and ECOG Performance Status	X	X	X	Within 72 hours of dosing. See protocol Appendix 3 for ECOG Performance Status scale		
Adverse Events Assessment		Continuously		Assessed using NCI CTCAE v.4		
Serious Adverse Event (SAE)		Continuously		Assessed using NCI CTCAE v.4		
Review of concomitant medications	X	X	X	-		
Laboratory Tests	See Note	See Note	See Note	XELOX: Within 72 hours prior to each dose. FOLFOX: Within 72 hours prior to each dose through Week 23 and every alternate dose thereafter. Include CBC w/differential, ALT, AST, total bilirubin, BUN or serum urea level, creatinine, Ca, Na, K, Cl, LDH and glucose. Note: Laboratory tests do not need to be repeated on C1D1 if performed within 14 days prior to first dose.		
Pregnancy Test (WOCBP only)	X	See Note	See Note	Serum or urine within 24 hours prior to the initial administration of study drug and then every 4 weeks (± 7 days) regardless of dose delays; if collected with a dosing visit, then obtain within 24 hours prior to administration of study drug: urine or serum.		

Table 5.1-4: On-Treatment Assessments - Subjects in Chemotherapy (XELOX or FOLFOX) Arm (CA209649)					
Procedure	FOLFOX Cycle 1 Day 1 (C1D1) Cycle 2 and beyond (Every 3 weeks) (Every 3 weeks)		FOLFOX Cycle 2 and beyond (Every 2 weeks) on Day 1	Note *Treatment till PD, unacceptable toxicity, withdraw from IC	
Efficacy Assessments					
Tumor Imaging Assessment		See Note	See Note	CT/MRI scan of chest, abdomen, pelvis, and any clinically indicated sites.	
				Every 6 weeks (± 7 days) from first dose up to and including Week 48, then every 12 weeks (± 7 days) regardless of treatment schedule until disease progression or the subject withdraws consent, whichever comes first. Subjects who discontinue study treatment for reasons other than PD will continue to have tumor assessments until their disease progresses or they withdraw consent. Use same imaging method as was used at screening/baseline	
Collection of biomarker sampling data					
Outcomes Research Assessments					
FACT-Ga	X			Assessed every 6 weeks (± 3 days) from C1D1,	
EQ-5D-3L	X	See Note	See Note	regardless of treatment schedule; if administered on a dosing day, assessment should take place prior to any other study procedures.	
Health Care Resource Utilization	X	X	X		

Table 5.1-4: On-Treatment Assessments - Subjects in Chemotherapy (XELOX or FOLFOX) Arm (CA209649)					
Procedure	XELOX and FOLFOX Cycle 1 Day 1 (C1D1)	XELOX Cycle 2 and beyond (Every 3 weeks) on Day 1	FOLFOX Cycle 2 and beyond (Every 2 weeks) on Day 1	Note *Treatment till PD, unacceptable toxicity, withdraw from IC	
Study Drug					
Randomization	X			Contact IRT for randomization	
Dispense Study Treatment	X	X	X	First dose to be administered within 3 calendar days after randomization. XELOX dose schedule: see Table 4.6.1-1. Subsequent	
				XELOX doses may be administered within dosing windows per package insert or local standard.	
				FOLFOX dose schedule: see Table 4.6.1-2. Subsequent FOLFOX doses may be administered within dosing windows per package insert or local standard.	
				Vials may be assigned up to 3 calendar days prior to every dose date.	

Table 5.1-5: Follow-Up Procedural Outline - All Subjects (CA209649)					
Procedure	Follow-up Visits 1 and 2 FU1: 30 days (± 7 days) after last dose FU2: 84 days (± 7 days) after FU1	Survival Follow-Up Visits every 3 months (± 14 days) from FU2	Notes		
Safety Assessments					
Physical Examination	X				
Adverse Events Assessment	X		Assessed using NCI CTCAE v.4		
Review of Subsequent Cancer Therapy	X	X	Additional subsequent cancer therapy details such as regimen, setting of the regimen, line of therapy, start date and end date of each regimen, best response to the regimen and date of progression after second line therapy will be collected.		
			The above information will be also collected during survival follow up period		
Review of Concomitant Medications	X				
Laboratory Tests	See Note		Include CBC w/differential, ALT, AST, total bilirubin, BUN or serum urea level, creatinine, Ca, Na, K, Cl, LDH and glucose.		
			If there are ongoing AE, monthly lab tests will be conducted till FU2.		
Pregnancy Test (WOCBP only)	See Note		Serum or urine, only for FU1, unless testing is required for a longer period, per local regulations.		
Efficacy Assessments					
Tumor Imaging Assessment	See Note	See Note	For subjects who discontinue study drug for reasons other than PD, follow-up scans should be performed every 6 weeks (± 7 days) up to and including Week 48, then every 12 weeks (± 7 days) until PD, lost to follow-up, or withdrawal of consent. Radiographic assessments should not be delayed until follow-up visits 1 & 2.		

Table 5.1-5: Follow-U	p Procedural Outline - A	all Subjects (CA209649)	
Procedure	Follow-up Visits 1 and 2 FU1: 30 days (± 7 days) after last dose FU2: 84 days (± 7 days) after FU1	Survival Follow-Up Visits every 3 months (± 14 days) from FU2	Notes
			CT/MRI scan of chest, abdomen, pelvis, and any clinically indicated sites.
			Use same imaging method as was used at screening/baseline.
Outcomes Research Assessments	·		
GaCS from the FACT-Ga	X		
FACT-G7	X	See Note	Every 3 months (± 14 days) after FU2, via a phone contact or in-person visit.
EQ-5D-3L	X		Commet of the person visits
Health Care Resource Utilization	X		
Collection of biomarker sampling			
Subject Status	•		
Survival status	X	X	Every 3 months (± 14 days) or more frequently as needed after FU2, may be accomplished by in-person visit or phone contact.

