1.1.4 Rationale for Dose Selection of Nivolumab-plus-Ipilimumab Treatment

The nivolumab-plus-ipilimumab combination dosing regimen selected for evaluation in this study is N1+I3 administered every 3 weeks (Q3W) for 4 doses followed by nivolumab 240 mg administered every 2 weeks (Q2W) until end of treatment (EOT).

The combination dosing of N1+I3 was selected based on its better clinical activity vs N3+I1 demonstrated in the CA209032 study (Table 1.1.2.1-2). Similar to CA209032, following the administration of 4 doses of the combination with ipilimumab, nivolumab will be administered alone at a flat dose of 240 mg Q2W starting at Week 13 until EOT.

Nivolumab 240 mg Q2W was selected based on clinical data as well as modeling and simulation approaches using population pharmacokinetics (PPK) and exposure-response analyses of data from studies in melanoma, NSCLC, and RCC, where body-weight normalized dosing (mg/kg) has been used.

PPK analyses have shown that the PK of nivolumab is linear with proportional exposure over a dose range of 0.1 to 10 mg/kg, and no differences in PK across ethnicities or tumor types were observed. Nivolumab clearance and volume of distribution were found to increase as the body weight increases, but less than proportionally with increasing weight, indicating that mg/kg dosing represents an over-adjustment for the effect of body weight on nivolumab PK. The PPK model previously developed using data from NSCLC subjects has recently been updated, using data from 1,544 subjects from 7 studies investigating nivolumab in the treatment of melanoma, NSCLC, and RCC. In this dataset, the median (minimum - maximum) weight was 77 kg (35 160 kg) and thus, an approximately equivalent dose of 3 mg/kg for an 80 kg subject, nivolumab 240 mg O2W, was selected for future studies. To predict relevant summary exposures of nivolumab 240 mg O2W, the PPK model was used to simulate nivolumab 3 mg/kg Q2W and 240 mg Q2W. The simulated patient populations consisted of 1000 subjects per treatment arm randomly sampled from the aforementioned pooled database of cancer subjects. Because no differences in PK were noted across ethnicities and tumor types, these simulated melanoma and NSCLC data will be applicable to subjects with other tumor types. The simulated measures of exposure of interest, time-averaged concentrations (Cavgss) for 240 mg Q2W, are predicted to be similar for all subjects in reference to 80 kg subjects receiving 3 mg/kg Q2W.

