4.6 Chemotherapy Arm Dosing

4.6.1 Oxaliplatin-Plus-Fluoropyrimidine Dose and Schedule

Subjects randomized to the chemotherapy arm should receive either XELOX or FOLFOX:

• Subjects assigned to XELOX will receive oxaliplatin 130 mg/m² administered IV on Day 1 of each treatment cycle and capecitabine 1000 mg/m² administered orally twice daily (ie, 1000 mg/m² in the morning and 1000 mg/m² in the evening) on Days 1 to 14 of each treatment cycle, every 3 weeks (see Table 4.6.1-1). Dosing windows for subsequent XELOX doses should adhere to recommendations in the current prescribing information or local standards, where indicated.

Premedication is not usually required in the first cycle. For subsequent cycles, adequate premedication may be administrated per local standard.

Capecitabine should be taken with food.

Table 4.6.1-1	Table 4.6.1-1: Dose Schedule of XELOX						
Treatment group	Drug name	Cycle 1 (Week 1)	Cycle 2 (Week 4)	Cycle 3 (Week 7)	Cycle 4 (Week 10)	Cycle 5 (Week 13) till EOT (Q3 weeks)	
XELOX	Capecitabine 1000 mg/m ² twice daily	Days 1 to 14	Days 1 to 14				
	Oxaliplatin 130 mg/m ²	Day 1	Day 1	Day 1	Day 1	Day 1	

• Subjects assigned to FOLFOX will receive oxaliplatin 85 mg/m², leucovorin 400 mg/m², and fluorouracil 400 mg/m² administered IV on Day 1 of each treatment cycle, and fluorouracil 1200 mg/m² IV continuous infusion over 24 hours daily or per local standard on Days 1 and 2 of each treatment cycle, every 2 weeks (see Table 4.6.1-2). Dosing windows for subsequent FOLFOX doses should adhere to recommendations in the prescribing information or local standards, where indicated.

Premedication is not usually required in the first cycle. For subsequent cycles, adequate premedication may be administrated per local standard.

Table 4.6.1-2	Table 4.6.1-2: Dose Schedule of FOLFOX					
Treatment group	Drug name	Cycle 1 (Week 1)	Cycle 2 (Week 3)	Cycle 3 (Week 5)	Cycle 4 (Week 7)	Cycle 5 (Week 9) till EOT (Q2 weeks)
FOLFOX	Oxaliplatin 85 mg/m ²	Day 1				
	Leucovorin 400 mg/m ²	Day 1				
	Fluorouracil 400 mg/m ²	Day 1				
	Fluorouracil 1200 mg/m ²	Days 1 & 2				

• No cross-over will be allowed between XELOX and FOLFOX in this study.

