5.3.2 On-Treatment Safety Assessments

Subjects will be evaluated for safety if they have received any study drug. Adverse event (AEs and SAEs) assessments will be continuous during the treatment phase as well as during the first two safety follow-up visits. Once subjects reach the survival follow-up phase, either in-person visits or documented telephone calls/email correspondence to assess the subject's status are acceptable.

Adverse events and laboratory values will be graded according to the NCI-CTCAE version 4.

The start and stop time of the study therapy infusions and any interruptions or infusion rate reductions should be documented.

Physical examinations are to be performed as clinically indicated. If there are any new or worsening clinically significant changes since the last exam, report changes on the appropriate non-serious or serious adverse event page.

On-treatment local laboratory assessments are to be completed within 3 calendar days prior to dosing: CBC with differential, LFTs (ALT, AST, total bilirubin), BUN or serum urea level, creatinine, Ca, Na, K, Cl, LDH and glucose.

Thyroid function testing (TSH with reflexive fT3 and fT4; Total T3/T4 are acceptable if Free T3/T4 are not available) is to be done every 6 weeks (± 7 days) starting at C1D1 (every 3 cycles for subjects receiving nivolumab at 240 mg Q2W and every 2 cycles for subjects receiving nivolumab at 360 mg Q3W or 480 mg Q4W).

On-treatment pregnancy tests should be performed as per the schedule in Table 5.1-2, Table 5.1-3, and Table 5.1-4.

Additional measures, including non-study required laboratory tests, should be performed as clinically indicated or to comply with local regulations. Laboratory toxicities (eg, suspected drug induced liver enzyme evaluations) will be monitored during the follow-up phase via on site/local labs until all study drug related toxicities resolve, return to baseline, or are deemed irreversible.

If a subject shows pulmonary-related signs (hypoxia, fever) or symptoms (eg, dyspnea, cough, or fever) consistent with possible pulmonary AEs, the subject should be immediately evaluated to rule out pulmonary toxicity, according to the suspected pulmonary toxicity management algorithm in the BMS-936558 (nivolumab) IB.

Some of the assessments referred to in this section may not be captured as data in the eCRF. They are intended to be used as safety monitoring by the treating physician. Additional testing or

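### After Week 23 the flow charts drop the pre-dose blood panel to every second FOLFOX dose, while the lab-based dosing rules stay unchanged and Section 5.3.2 does not mention the reduction

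*Protocol*

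**What the plan says.** Protocol Section 5.1, Table 5.1-4 (chemotherapy arm), sets the laboratory panel as "FOLFOX: Within 72 hours prior to each dose through Week 23 and every alternate dose thereafter". Table 5.1-3 has the same rule for the combination arm: "Nivolumab + FOLFOX: Within 72 hours prior to each dose through Week 23 and every alternate dose thereafter". The panel includes CBC with differential, ALT, AST, total bilirubin and creatinine. In both tables XELOX subjects have it before every dose, with no later reduction.

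FOLFOX itself does not slow down. The last column of Table 4.6.1-2 is headed "Cycle 5 (Week 9) till EOT (Q2 weeks").

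Section 5.3.2 describes on-treatment labs this way: "On-treatment local laboratory assessments are to be completed within 3 calendar days prior to dosing: CBC with differential", followed by liver tests, creatinine and the rest of essentially the same panel. It mentions neither Week 23 nor alternate doses. For thyroid tests the same section does spell out a lower frequency: "every 3 cycles for subjects receiving nivolumab at 240 mg Q2W and every 2 cycles for subjects receiving nivolumab at 360 mg Q3W".

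Two other schedules help to place the rule. Table 5.1-2 has the same reduction for nivolumab plus ipilimumab ("Within 72 hours prior to each dose through Week 23 visit and every alternate dose thereafter"), but by then those subjects are on nivolumab only: Section 1.1.4 says "nivolumab will be administered alone at a flat dose of 240 mg Q2W starting at Week 13 until EOT". For nivolumab 480 mg Q4W alone, footnote a of Table 5.1-3 has procedures "aligned with dosing visits (every 4 weeks on Day 1). Laboratory test should be done prior each dose".

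**The concern.** Several dosing rules depend on these results, and none is relaxed with time on treatment:

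- Table 4.6.2.3-2 interrupts FOLFOX for Grade 3 or greater neutropenia and for Grade 2 or greater thrombocytopenia.
- Section 4.7 stops chemotherapy on liver-test thresholds, and stops oxaliplatin when creatinine clearance falls below 30 mL/min.
- In the nivolumab plus FOLFOX group, Section 4.5.1.2 delays nivolumab for Grade 2 drug-related creatinine, AST, ALT or bilirubin changes. Section 4.5.2.2 extends a delay to the whole regimen, while allowing one component to continue when the toxicity does not overlap.

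A site that follows the flow charts exactly has no current result against which to apply these rules at every second late dose. A new abnormality without symptoms could then go unseen at a dose of myelosuppressive chemotherapy. A site that takes its lab timing from Section 5.3.2 may test before every dose, so practice could differ between sites.

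**Working it through.** The plan gives no figure of its own on this point. The check is schedule arithmetic, assuming doses are given on time.

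**Dose grid.** Dose week = 1 + 2 × (cycle − 1). This reproduces Table 4.6.1-2 (Weeks 1, 3, 5, 7, 9). Week 23 is Cycle 12, since 1 + 2 × 11 = 23.

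**Doses without a scheduled panel.** From Week 25 to Week 47 there are (47 − 25)/2 + 1 = 12 doses.
- If the first alternate-dose panel is at Week 27, panels fall at Weeks 27, 31, 35, 39, 43 and 47. Weeks 25, 29, 33, 37, 41 and 45 have none: 6 of 12.
- If alternation starts at Week 25 instead, Weeks 27, 31, 35, 39, 43 and 47 have none: again 6 of 12.
- Carried on to Week 103, the count is 20 of 40.

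**Intervals.**

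| Treatment | Dosing interval | Scheduled lab interval | Doses with a panel |
|---|---|---|---|
| FOLFOX through Week 23 | 14 days | 14 days | all |
| FOLFOX after Week 23 | 14 days | 2 × 14 = 28 days | 1 in 2 |
| XELOX | 21 days | 21 days | all |
| Nivolumab 480 mg Q4W alone | 28 days | 28 days | all |

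At a skipped dose the latest scheduled result is 14 days old, or up to 14 + 3 = 17 days with the 72-hour window, and one FOLFOX dose has been given since.

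**Who can still be reached.** The Week 25 dose falls 24 × 7 = 168 days after the first.
- Revised Protocol 09 is dated 16-Sep-2019; 168 days earlier is 1-Apr-2019. Subjects first dosed by then had already reached Week 25 if they were still on treatment.
- Accrual ended in May 2019 (Section 8.1.1). Taking 31-May-2019 as the latest first dose (an assumption), the last subjects reach Week 25 by about 15-Nov-2019.

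**Is late FOLFOX rare by design?** 168/30.4375 = 5.52 months. Under the PFS hazards assumed in Table 8.1.4-1:
- Control: exp(−(0.09 × 3 + 0.17 × 2.52)) = exp(−0.698), about 50% progression-free.
- Combination, 6-month delay: the same, about 50%.
- Combination, 3-month delay: exp(−(0.27 + 0.56 × 0.428)) = exp(−0.510), about 60%.

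These are planning assumptions about progression. They do not count subjects on FOLFOX: XELOX users and those who stopped for toxicity are not separated out. They show only that the schedule after Week 23 is not a remote case.

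**The case against.** The strongest reply is that nothing here is inconsistent. Section 5.3.2 gives a window and a panel and speaks of dosing in general, without saying that every dose is meant. The tables supply the frequency, and Section 3.1.2 sends the reader to them for study assessments. Section 5.3.2 is not a full schedule in other respects either: it leaves physical examinations to clinical need, while the tables require one at each dose. On that reading the reduction is deliberate. A reader might infer a flat contradiction between text and tables, and the documents do not support that. What stands is an ambiguity: Section 5.3.2 is silent on the reduction although it details the thyroid frequency.

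The second reply is that the tables are a minimum. Chemotherapy administration follows local standards (Section 3.1.2), the FOLFOX modifications are recommendations that may give way to local practice (Sections 4.6.2 and 4.6.2.3), and Section 5.3.2 provides for further tests when clinically needed. Examination, vital signs and ECOG status are checked at every dose. A known cytopenia must resolve to a stated grade before treatment resumes, which in practice means a repeat count. All of this narrows the gap to new abnormalities without symptoms in subjects who have already had 12 monitored doses. It does not close the gap, because none of it requires a count at the skipped doses and an examination does not measure neutrophils, platelets or creatinine. The liver and renal stopping criteria in Section 4.7 are also worded as requirements.

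Third, the calendar comparison is mild: 28 days against 21 for XELOX, and equal to nivolumab 480 mg Q4W alone. That is correct. The difference that matters is per dose, since only late FOLFOX gives chemotherapy with no scheduled panel before it.

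**Conclusion.** The point holds as a modest patient-safety and clarity issue. Under Tables 5.1-3 and 5.1-4, half of the FOLFOX doses after Week 23 (6 of 12 in Weeks 25 to 47) carry no scheduled count, liver test or creatinine, while the rules that need those results continue unchanged. The protocol gives no reason for reducing monitoring during chemotherapy. The matching rule in the nivolumab plus ipilimumab arm does not supply one, because it applies to nivolumab alone.

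The count assumes on-schedule dosing and a site that does no more than the tables ask. The number of subjects affected is unknown, since the documents give neither the FOLFOX share nor the time on FOLFOX, and at this version's date it is limited to those still receiving the regimen. A reader might infer that patients were in fact dosed without current results; the documents show only what is scheduled, and local practice may well have been stricter. Alpha, power and sample size are not affected.

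**What to change.** In Tables 5.1-3 and 5.1-4, require CBC with differential, ALT, AST, total bilirubin and creatinine within 72 hours before each dose for as long as any FOLFOX component is given, as is done for XELOX. Keep the alternate-dose reduction after Week 23 only for nivolumab 240 mg Q2W alone; that leaves a 28-day interval, the same as for 480 mg Q4W alone. Amend Section 5.3.2 to state both: labs within 3 calendar days before each dose, and before alternate doses after Week 23 only for Q2W nivolumab alone.

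The cost is a wording change in two tables and one section, by amendment or administrative letter, plus one extra local blood draw per 4 weeks at an infusion visit the subject already attends. With accrual complete, it benefits only subjects still on FOLFOX.
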